9.4.3 Safety Analyses

N/A

9.4.4 Baseline Descriptive Statistics

In this pilot study, various descriptive statistics will be used to describe and compare baseline patient demographics per group.

9.4.5 Planned Interim Analyses

None planned at this time

9.4.6 Sub-Group Analyses

The primary, secondary and exploratory endpoints will be analyzed within group stratified for age in order to determine if there is evidence of a differential response in the setting of immunosenescence.

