4 STUDY DESIGN

4.1 OVERALL DESIGN

Hypothesis

The major hypothesis of this single-site pilot study is that recruitment of antigen-specific T cells and innate immune cell subsets following bronchoscopic instillation of purified protein derivative (PPD) from *M. tuberculosis* into the lung will occur primarily in individuals with latent TB infection. These Mtb-specific T cell responses will occur only in the segments into which PPD was instilled and not in the control lung segments. Lastly, pulmonary immune cell activation and number will peak early after PPD instillation and subsequently wane both in the airways and peripheral blood. These responses will be much more pronounced in the local pulmonary micro-environment as opposed to the systemic vasculature.

Using PET-CT imaging after PPD instillation, we hypothesize that it will be possible to identify increased cellular activity in draining thoracic lymph nodes, as well as in the pulmonary parenchyma. Furthermore, we expect that the above signals we are able to discern will progressively wane in the weeks following bronchoscopic PPD instillation.

Longitudinal Study Design

We plan to screen up to 100 non-LTBI controls vs confirmed LTBI to enroll up to 25 individuals in order to have a total of 20 individuals who are concordant on the PPD and IGRA test complete the study as follows:

Group A (LTBI Group): 13 PPD + and IGRA + subjects

[figure not shown]
Group B (non-LTBI Group): 7 PPD - and IGRA - subjects

We seek to enroll individuals at a 2:1 ratio of Group A:Group B in order to maximize the data derived from individuals with latent TB who will mount antigen-specific T cell responses post PPD instillation. This strategy will also decrease variance in Group A via relative oversampling compared to Group B.

Figure 1 outlines the experimental timeline. A baseline PET-CT study of the thoracic cavity will be obtained, and the first bronchoscopy will be performed in the following the week to collect the baseline BAL sample and to instill the PPD as outlined above. Peripheral blood will be collected at the time of each bronchoscopy procedure before the BAL. To examine early immune responses, on approximately day 4 the second PET-CT study will be obtained and the following day a second BAL will be performed, and peripheral blood samples will be collected. BAL will be done first in the control anterior segment of the left upper lobe and then again in the

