5.1 INCLUSION CRITERIA

Adults 18-64 years old will be recruited for the two groups (non-LTBI controls vs confirmed LTBI). The lower limit of this age range is based on the need for invasive bronchoscopic

procedures and exposure to radiation, both of which carry more risk at younger ages. In addition, most adults present with post-primary or reactivation TB that most often occurs radiographically in the upper lobes of the lungs, often with cavitation. Conversely, children and rare adults with primary TB have non-cavitary disease in the lower lobes. The higher limit of this age range is based on the known property of immune senescence, i.e., the waning of the strength of immune responses with advancing age.

In order to be eligible to participate in this study, an individual must meet all of the following criteria:

1. Ability of subject to understand and the willingness to sign a written informed consent document.
2. Stated willingness to comply with all study procedures and availability for the duration of the study
3. Male or female, aged 18 – 64 years of age
4. No significant active medical problems. This would include but not limited to any cardiac disorder (e.g. arrhythmia, valvular disease), pulmonary disease (e.g. asthma requiring chronic medications, chronic bronchitis, emphysema, obstructive sleep apnea), kidney disease (e.g. nephritis, nephrosis), rheumatologic disorder (e.g. inflammatory arthritis), endocrine disorder (e.g. diabetes, thyroid disease), liver disease (e.g. hepatitis), gastrointestinal disorder (e.g. inflammatory bowel disease) or infectious disease (e.g. active tuberculosis).
5. For females of reproductive potential: use of highly effective contraception for at least 1 month prior to screening and agreement to use such a method during study participation
6. For males of reproductive potential: use of condoms or other methods to ensure effective contraception with partner and agreement to use such a method during study participation

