9.2 SAMPLE SIZE DETERMINATION

This is a pilot study which will be hypothesis-generating in nature. For this reason we will not be pursuing the formal sample size calculation that corresponds to a specified statistical power. However, the sample size of 13 confirmed LTBI cases and 7 confirmed non-LTBI controls (a total of 20 subjects) is slightly larger than those of the original studies of the current bronchoscopic instillation model pioneered by Silver and colleagues (21-23). Silver's 2003, 2005 and 2011 PPD bronchoscopic instillation studies included a total of 9, 15, and 14 total subjects respectively. Each study was able to demonstrate a statistically significant increase in the frequency of Mtb-specific CD4+ T cells in the BAL of LTBI subjects as compared to the BAL of non-LTBI controls within each study. Furthermore, we anticipate that our immunological signals will likely stand out due to confirmation of LTBI status using concordant TST and IGRA testing. We will enroll up to an additional 5 subjects in order to achieve 20 completed studies.

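### Section 9.4.6 splits groups of 13 and 7 into undefined age strata; continuous age with group-specific slopes would use the same data better

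*Combined protocol and SAP*

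**What the plan says.** Section 9.4.6 (Sub-Group Analyses) commits to a method. The primary, secondary and exploratory endpoints "will be analyzed within group stratified for age", to see whether response differs in the setting of immunosenescence. It does not say how many strata there are, where they are cut, or which test or estimate is compared across them.

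The group sizes are fixed in section 4.1: "Group A (LTBI Group): 13 PPD + and IGRA + subjects" and "Group B (non-LTBI Group): 7 PPD - and IGRA - subjects". Section 9.2 adds "We will enroll up to an additional 5 subjects in order to achieve 20 completed studies", so 13 and 7 are the numbers expected at analysis.

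Sections 9.4.1 and 9.4.2 plan repeated-measures mixed models comparing LTBI with non-LTBI for the primary and secondary endpoints. Age appears in neither. Section 9.4.6 is therefore the only place where age is analysed.

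Section 5.1 limits entry to ages 18-64 and explains the upper bound: "The higher limit of this age range is based on the known property of immune senescence".

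**The concern.** Age is known exactly for every participant. Cutting it into strata discards part of that information, and doing so inside groups of 13 and 7 leaves cells too small to say much. Because the strata are undefined, the cut could also be chosen after the data are seen.

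At stake is whether the age analysis yields anything readable. Each participant undergoes three bronchoscopies and three PET-CT scans, so the age information should be used as fully as the design allows.

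**Working it through.** **The plan's own figures.** 13 + 7 = 20, as in section 9.2. A 2:1 ratio applied to 20 gives 13.3 and 6.7, which rounds to 13 and 7. No power, alpha, effect size or stratum size is stated, so there is no power figure to reproduce. Two-sided 5%, the correlations and the age distributions below are assumptions.

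**Stratum sizes.**
- Two strata at each group's own median: 3 and 4 controls; 6 and 7 LTBI.
- Three strata: 2-3 controls; 4-5 LTBI.
- Four strata: 1-2 controls; 3-4 LTBI.
- One pre-set cut, each control having a 50% chance of being in the older stratum: P(a control stratum holds 2 or fewer) = 2 × (1 + 7 + 21)/128 = 45%; P(1 or fewer) = 2 × (1 + 7)/128 = 12.5%. If the chance is 30%, these become 68% and 33%.

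The 3-and-4 split is therefore the best case.

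**Precision in the best case.** The 95% interval half-width for a difference between two strata, in SD units, is t(0.975, n1+n2−2) × √(1/n1 + 1/n2).
- Controls, 3 vs 4: 2.571 × √(1/3 + 1/4) = 1.96 SD. A t-test needs a difference of about 2.7 SD for 80% power.
- LTBI, 6 vs 7: 2.201 × √(1/6 + 1/7) = 1.22 SD. The corresponding difference is about 1.7 SD.

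**Information lost by a median split.** The squared correlation between age and its above-median indicator is 0.75 for uniform ages and 2/π = 0.64 for normal ages. That is the largest share of the age variance a median split retains.

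**Power, median split vs continuous age.** Simulation with one summary response per participant, a linear age effect, uniform ages and normal errors. The comparison is a two-sample t-test on the split against a t-test on the slope.

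| Age-response correlation | Controls (n=7): split vs continuous | LTBI (n=13): split vs continuous |
|---|---|---|
| 0.5 | 14% vs 22% | 31% vs 44% |
| 0.6 | 19% vs 31-32% | 44-45% vs 63-64% |
| 0.7 | 27% vs 48% | 62% vs 84% |

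Ranges show variation between simulation runs.

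**How the age term should enter a joint model.** Sections 4.1 and 9.1 expect the response mainly in LTBI, so an age slope may exist only there. With correlation 0.6 in LTBI and none in controls:
- a single common age slope over all 20 has about 46% power, little better than the LTBI-only split;
- a separate LTBI slope in the joint model has about 66%;
- the group-by-age difference has about 28% (19% at correlation 0.5, 42% at 0.7).

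Group-specific slopes keep the gain, and a common slope can lose it.

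**The case against.** The strongest defence is that this is one subgroup sentence in a study that section 9.2 calls a hypothesis-generating pilot with no power calculation. No decision rests on it. Continuous age does not rescue the question either: with 7 controls power is only about 31-32% at correlation 0.6, and the difference between slopes stays poorly estimated. The gain also assumes a roughly linear trend. All of this stands. It limits the severity and is why the result should be labelled descriptive, but it gives no reason to prefer strata.

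Three stronger readings are tempting, and the documents do not support them.

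- *The control analysis can never reach 5%.* With 3 vs 4, the smallest two-sided exact rank p-value is 2/35 = 0.057. But no rank test is planned: 9.4.1 and 9.4.2 specify mixed models with a transformation if needed, and 9.4.6 names no test. A t-test has no such floor.
- *One age slope over all 20 solves the problem.* If both groups shared a slope at correlation 0.6, power would be about 83% against 63% for the split. That assumption conflicts with the plan's own expectation of responses mainly in LTBI.
- *The cap at 64 removes the range of interest.* Section 5.1 describes immune responses waning with advancing age and does not say that this begins at 64. A trend within 18-64 is a coherent target; what cannot be done is to extend it above 64.

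**Conclusion.** The point holds as a minor one. Section 9.4.6 uses undefined age strata within groups of 13 and 7. At best this gives 3 and 4 controls and 6 and 7 LTBI participants, and it discards at least a quarter of the age variance if ages are uniform. At correlation 0.6, continuous age adds about 12-13 percentage points of power in controls and about 19 in LTBI.

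These sizes rest on assumptions the documents do not supply: a linear age effect, uniform ages, normal errors with equal variance in the two groups for the joint model, and repeated measures reduced to one response per participant. The cell of 3-4 controls is likewise not a figure in the plan; it follows from assuming two strata at the control median. Under any of these choices the age result remains descriptive.

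**What to change.** In 9.4.6, replace stratification with continuous age and a group-by-age term in the mixed models already planned. Report the age slope in LTBI, the age slope in non-LTBI and their difference, each with a 95% confidence interval and labelled descriptive. Do not rely on a common slope. Name the visit to which the slopes refer. For the exploratory endpoints, which 9.4.8 handles by numerical and graphical summaries, a plot of response against age by group is enough. Add that the results describe age trend within 18-64 only.

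The cost is a few sentences of text, with no extra participants, visits or assays. The price is a linearity assumption, to be checked with the same scatter plots, and the difference between slopes will remain imprecise. If strata are kept for display, their number and cut-points should be fixed before the data are analysed.

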9.4.7 Tabulation of individual Participant Data

Each individual participant data will be listed by measurement evaluated, location of measurement acquisition and day of measurement acquisition relative to bronchoscopic challenge date.

9.4.8 Exploratory Analyses

For the exploratory hypotheses, both numerical and graphical summary tools will be used to study the phenotypic and functional analysis of immune cell populations in the airways and

circulation of individuals with or without LTBI. Also, descriptive statistics will be used to characterize the production of soluble mediators in BAL fluid and blood.

10 REGULATORY AND OPERATIONAL CONSIDERATIONS

10.1 INFORMED CONSENT PROCESS

10.1.1 Consent/Assent Procedures and Documentation

Informed Consent Processes and Procedures

Informed consent will be conducted following OHSRP Policy 301. An IRB-approved consent form, will be provided to the subject electronically or by hard copy for review prior to consenting. The initial consent process as well as re-consent, when required, may take place in person or remotely (e.g., via telephone, telehealth or other NIH approved platforms). The investigational nature and objectives of this trial, the procedures, and their attendant risks and discomforts and potential benefits will be carefully explained to the subject in a private setting. The subject will be given as much time as they need to review the document and to consult with their family, friends, and personal health care providers. In addition, a study team member will be available to answer any questions.

A signed and dated informed consent document will be obtained by any investigator authorized to consent (See Key Study Personnel) prior to entry onto the study. Consent may be obtained with required signatures on the hard copy of the consent or on the electronic document.

When a document that is in electronic format is used for obtaining consent, this study may use the iMed platform which is 21 CFR, Part 11 compliant, to obtain the required signatures.

During the consent process, participants and investigators may view the same approved consent document simultaneously when participant is being consented in person at the Clinical Center or both may view individual copies of the approved consent document on screens in their respective locations remotely. Signatures may be obtained either by both directly signing on the device that the consenting investigator is using (when in person) or through iMed Mobile Signature Capture (remotely) which allows texting or emailing a link to the participant. That link allows the participant to review the consent, then proceed to sign on the device they are using.

Whether hard copy or electronic, both the investigator and the participant will sign the document with a hand signature using a pen (if using hard copy), finger, stylus, or mouse (if electronic).

When done remotely, if the participant prefers to sign a hard copy, they may be instructed to sign and date the consent document during the discussion and mail, secure email or fax the signed document to the consenting investigator.

Whether in person or remote, the privacy of the subject will be maintained.

The fully signed informed consent document will be stored in the electronic medical record, and the subject will receive a copy of the signed informed consent document.

10.1.2 Consent for minors when they reach the age of majority

Not applicable.

10.1.3 Telephone and or Telehealth platform consent

Participants may be contacted by telephone and or Telehealth NIH- approved platform per Policy 303 to obtain informed consent. For initial consent and for subjects actively participating in the study who may need to be re-consented due to changes to the informed consent or procedures.

10.1.4 Telephone child assent

Not applicable

10.1.5 Participation of Subjects who are/become Decisionally Impaired

Not applicable. Adults who are unable to provide initial informed consent will be excluded.

10.2 STUDY DISCONTINUATION AND CLOSURE

This study may be temporarily suspended or prematurely terminated if there is sufficient reasonable cause. Written notification, documenting the reason for study suspension or termination, will be provided by the suspending or terminating party to study participants. If the study is prematurely terminated or suspended, the Principal Investigator (PI) will promptly inform study participants, the Institutional Review Board (IRB), and sponsor and will provide the reason(s) for the termination or suspension. Study participants will be contacted, as applicable, and be informed of changes to study visit schedule.

Circumstances that may warrant termination or suspension include, but are not limited to:

- Determination of unexpected, significant, or unacceptable risk to participants
 - a. A single SAE in a subject that is assessed as related or possibly related to the study drug
 - b. Grade 3 or higher laboratory abnormality in 3 or more subjects with a reasonable possibility of a causal relationship to the administration of study drug
 - c. Grade 3 or higher with the same or similar Adverse Event in 2 or more subjects assessed as possibly related to study drug.
 - d. Will restart study if investigation determines study drug not to be the cause
- Insufficient compliance to protocol requirements
- Data that are not sufficiently complete and/or evaluable
- Determination that the primary endpoint has been met

Study may resume once concerns about safety, protocol compliance, and data quality are addressed, and satisfy the sponsor, IRB and/or Food and Drug Administration (FDA).

10.3 CONFIDENTIALITY AND PRIVACY

Participant confidentiality and privacy is strictly held in trust by the participating investigators and their staff. This confidentiality is extended to cover testing of biological samples and genetic tests in addition to the clinical information relating to participants. Therefore, the study protocol, documentation, data, and all other information generated will be held in strict confidence. No information concerning the study or the data will be released to any unauthorized third party without prior written approval of the sponsor.

All research activities will be conducted in as private a setting as possible.

The study monitor, representatives of the Institutional Review Board (IRB), and/or regulatory agencies may inspect all documents and records required to be maintained by the investigator, including but not limited to, medical records (office, clinic, or hospital) and pharmacy records for the participants in this study. The clinical study site will permit access to such records.

The study participant's contact information will be securely stored at each clinical site for internal use during the study. At the end of the study, all records will continue to be kept in a

secure location for as long a period as dictated by the reviewing IRB, Institutional policies, or sponsor requirements.

Study participant research data, which is for purposes of statistical analysis and scientific reporting, will be transmitted to and stored at the [name] Lab data server. This will not include the participant's contact or identifying information. Rather, individual participants and their research data will be identified by a unique study identification number. The study data entry and study management systems used will be secured and password protected. At the end of the study, all study databases will be de-identified and archived at the [name] Lab data server.

To further protect the privacy of study participants, a Certificate of Confidentiality has been issued by the National Institutes of Health (NIH). This certificate protects identifiable research information from forced disclosure. It allows the investigator and others who have access to research records to refuse to disclose identifying information on research participation in any civil, criminal, administrative, legislative, or other proceeding, whether at the federal, state, or local level. By protecting researchers and institutions from being compelled to disclose information that would identify research participants, Certificates of Confidentiality help achieve the research objectives and promote participation in studies by helping assure confidentiality and privacy to participants.

10.4 FUTURE USE OF STORED SPECIMENS AND DATA

After analyzing the biospecimens for primary research purposes as described in the protocol, remaining samples suitable for future research will be stored in the Principal Investigator's laboratory freezers in a coded manner to ensure data protection. Biospecimens may be destroyed only when permitted by the clinical director and approved by the IRB. Any future research use of biospecimens not defined in the research protocol in which NHLBI investigators are engaged in research (e.g., they are undertaking research activities and hold the key that identifies research subjects) requires IRB review and approval. Coded biospecimens (NHLBI investigators hold the key that identifies research subjects) to be shared outside of NIH for future research use where results will not be returned to the Principal Investigator does not require IRB review. Refusal of a research subject participant to allow for future use of biospecimens will be honored.

10.5 SAFETY OVERSIGHT

Safety oversight will be under the direction of a Data and Safety Monitoring Board (DSMB) composed of individuals with the appropriate expertise. Members of the DSMB should be independent from the study conduct and free of conflict of interest, or measures should be in place to minimize perceived conflict of interest. The DSMB will meet at least annually to assess safety and efficacy data on each arm of the study. The DSMB will operate under the rules of an approved charter.

10.6 CLINICAL MONITORING

Principal Investigator:

Accrual will be monitored by the principal investigator who will provide oversight and will monitor accrual and safety data. The investigator (and/or designee) will make study documents (e.g., consent forms and pertinent hospital or clinical records) readily available for inspection by

the local IRB and the NHLBI Office of the Clinical Director staff for confirmation of the study data.

The monitoring of this study will be conducted by clinical research associates (CRAs)/monitors employed by an independent contract organization working under an agreement with NHLBI to monitor aspects of the study in accordance with the appropriate regulations and the approved protocol. The objectives of a monitoring visit will be: 1) to verify the existence of signed informed consent form (ICF) and documentation of the ICF process for each monitored subject; 2) to verify the prompt and accurate recording of all monitored data points, and prompt reporting of all SAEs; 3) to compare abstracted information with individual subjects' records and source documents (subject's charts, laboratory analyses and test results, physicians' progress notes, nurses' notes, and any other relevant original subject information); and 4) to help ensure investigators are in compliance with the protocol. The monitors also will inspect the clinical site regulatory files to ensure that regulatory requirements (Office for Human Research Protections-OHRP) and applicable guidelines (ICH-GCP) are being followed. Monitoring will be conducted according to the OCD schedule. During the monitoring visits, the investigator (and/or designee) and other study personnel will be available to discuss the study progress and monitoring visit.

The investigator (and/or designee) will make study documents (e.g., consent forms and pertinent hospital or clinical records readily available for inspection by the local IRB, the site monitors, and the NHLBI staff for confirmation of the study data.

